6.13.4.5. Allergic/Hypersensitivity Reactions

Listings of allergic/hypersensitivity AEs will be generated. If the number of patients with these events is 3% or more, then, a summary report will also be generated by each randomized treatment group.

A similar summary and listing will be generated for patients with injection site reactions.

6.13.4.6. Supraventricular Arrhythmias and Cardiac Conduction Disorders

Summaries of these AESIs will be produced by PT with decreased frequency and by each randomized treatment using SMQ. The data listing will be generated. The qualitative ECG data including conduction and arrhythmia will be summarized by each randomized treatment and listed by treatment and patient.

6.13.5. Gastrointestinal Safety

Because certain GI AEs, including nausea, vomiting, and diarrhea, are among the most common events reported in patients treated with dulaglutide, summaries and analyses for incidence will be provided for each randomized treatment, dulaglutide 3.0 mg/algorithm 1, dulaglutide 3.0

mg/algorithm 2, dulaglutide 4.5 mg/algorithm 1, dulaglutide 4.5 mg/algorithm 2, algorithm 1, algorithm 2 during the 18-week treatment period and during the first 6 weeks (titration phase), overall, and by visit, to compare the effects of the 4 different dose escalations (2 algorithms for each of the 2 investigational doses) and effects of the 2 titration algorithms on GI tolerability, as well as the overall effects of randomized treatments.

The prevalence of GIs, as well as the incidence of the first occurrence of nausea and/or vomiting will be summarized separately by the treatment and the time interval of interest mentioned in the first paragraph.

The maximum severity and duration from baseline to Week 18 of nausea and/or vomiting TEAEs will be summarized by the aforementioned treatments.

The time course plot on the initiation of nausea regardless of severity (prevalence) will be generated for each treatment. The y-axis is the % subjects with nausea and the x-axis is the time since the first dose.

If data warrant, a negative binomial model similar to the rate of hypoglycemia analysis may be implemented for each of the aforementioned parameters.

A listing with treatment-emergent GI AEs of interest will be provided.

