#### **Titration Phase (end of Visit 3 to Visit 6)**

During the titration phase in the investigational dose dulaglutide arms, the dose of dulaglutide will be escalated according to 1 of 2 algorithms:

- Algorithm 1: patients will receive dulaglutide 1.5 mg once weekly for the first 4 weeks followed by dulaglutide 3.0 mg once weekly for the next 2 weeks, or
- Algorithm 2: patients will receive dulaglutide 0.75 mg once weekly for the first 2 weeks followed by dulaglutide 1.5 mg once weekly for the next 4 weeks.

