## 5.4. Scientific Rationale for Study Design

Study GBGJ utilizes the parallel arm design as an appropriate option to collect data attributable to a specific randomized therapy without potential interference from other randomized treatments or the randomization sequence.

The 2 investigational dulaglutide doses (once weekly 3.0 mg and 4.5 mg) to be studied in this trial were chosen based on simulations which included data collected in Studies GBCD and GBCF (Barrington et al. 2011; Skrivanek et al. 2014), among other studies. Further details and the rationale for the choice of the doses are provided in Sections 3.2 and 5.5. The placebo comparator is considered appropriate for this trial to establish effects of the investigational doses on efficacy and safety measures that are attributable to dulaglutide. The active comparator dulaglutide 1.5 mg dose has been chosen to enable comparison of data collected under similar conditions to the investigational doses. Due to small sample size, the comparison between investigational doses and the dulaglutide 1.5 mg dose will use exploratory assessments with Bayesian-based methods to guide dose selection for Phase 3 development and design of confirmatory trials.

The 2 titration algorithms to be used in the dulaglutide 3.0 mg and 4.5 mg arms have been chosen based on simulations that included data from several Phase 2 and Phase 3 trials to assess the potential mitigating effect of doubling increases in titrated doses (ie, Algorithm 1) versus longer exposure at lower titration doses (ie, Algorithm 2). They differ with respect to the initial dose (0.75 mg or 1.5 mg) corresponding to the recommended starting doses in different country-specific labels, number of dose steps (2 or 3), and duration of exposure at the initiation dose (2 or 4 weeks). The exposure-response information for GI tolerability collected from this study will be combined with information from previous studies to guide design of the final algorithm to determine the starting dose(s), titration step(s), and duration of titration, to be taken into Phase 3 development if data suggests dose titration is necessary.

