### **7.2.1. Selection and Timing of Doses**

Patients will be allocated to 1 of the 3 dulaglutide doses (4.5 mg, 3.0 mg, or 1.5 mg) or placebo, each administered once weekly as subcutaneous injection(s). Rationale for the choice of the 2 investigational doses (4.5 mg and 3.0 mg) is provided in Section [5.5](#). The dulaglutide 1.5 mg dose was chosen as the active comparator since this is the highest dose approved by regulatory agencies. The randomization strategy is described in Section [7.2](#).

During the titration phase (end of Visit 3 to Visit 6 [Weeks 0 to 5]), patients assigned to investigational-dose dulaglutide (3.0 mg or 4.5 mg) will begin treatment using Algorithm 1 or Algorithm 2 (Table GBGJ.2). Patients assigned to dulaglutide 1.5 mg or placebo will begin administering treatment as assigned at Visit 3, without titration. During the maintenance phase (end of Visit 6 to Visit 12 [Weeks 6 to 17]), all patients will administer study drug at their final assigned dose. The assigned doses during the titration and maintenance periods may not be dextitratid. Patients with poor tolerability of the study treatments will be allowed to discontinue dosing temporarily (Section 8.1.2). Patients who discontinue study treatment temporarily and are then unable to tolerate it upon rechallenge will be discontinued from study drug and will be initiated on glycemic rescue therapy (Section 8.1.1).

It is recommended that patients inject the study drug at approximately the same time of day on the same day each week. For doses requiring multiple injections, the entire dose (all injections for that week) should be administered on the same day, within 30 minutes. The day and time of all dose administrations are to be recorded in diaries by the patients. If 1 or more injections are not given on the scheduled day, the missed injection(s) should be given as soon as possible after the scheduled day if there are at least 3 days (72 hours) until the next dose. If fewer than 3 days remain before the next scheduled dose, the missed injection(s) should be skipped and the next dose given at the regularly scheduled day and time.

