5.2. Determination of Sample Size

Assuming a screen failure rate of 30%, approximately 429 patients will need to be screened to attain approximately 300 patients randomized to the 4 treatment arms in a 1:1:1:1 ratio for 4.5 mg, 3.0 mg, 1.5 mg dulaglutide, or placebo weekly (~75 patients per arm). For the investigational dulaglutide dose arms (4.5 mg and 3.0 mg), approximately 38 patients will be assigned to each titration algorithm (Algorithms 1 and 2). Assuming a 20% dropout, this will result in approximately 60 patients per arm and 30 patients per algorithm (in each of the investigational-dose dulaglutide arms) completing the study.

The aforementioned sample size provides $\geq 90\%$ power to demonstrate superiority for the dulaglutide doses (4.5 mg, 3.0 mg, and 1.5 mg) to placebo with respect to HbA1c change from baseline to 18 weeks. This assumes a true glycemic effect difference of -1% HbA1c for each dulaglutide dose versus placebo, and a standard deviation (SD) of 1.2% with a 2-sided alpha of 0.05.

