5.3. Method of Assignment to Treatment

Patients who meet all criteria for enrollment will be randomized to one of the study treatment arms at Visit 3. Assignment to treatment arms will be determined by a computer-generated random sequence using an Interactive Web Response System (IWRS). The IWRS will be used

to assign cartons containing double-blinded study drug to each patient. Site personnel will confirm that they have located the correct cartons by entering a confirmation number found on the label into the IWRS.

Block randomization will be used at the country level. Patients will be randomized in a 1:1:1:1 ratio (dulaglutide 4.5 mg, dulaglutide 3.0 mg, dulaglutide 1.5 mg, placebo). Within the dulaglutide 4.5 mg and 3.0 mg arms, patients will be randomly assigned (1:1) to Algorithm 1 or Algorithm 2. Randomization will be stratified by HbA1c (<8%, \geq 8%).

6. A Priori Statistical Methods

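### Through Week 3 both Algorithm 1 cells and the 1.5 mg arm are on the same regimen, and the GI tables could pool them: about 150 v 75 patients on starting dose instead of about 75 v 75

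*SAP*

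**What the plan says.** **Regimens.** Protocol 5.1 (Titration Phase) states: "Algorithm 1: patients will receive dulaglutide 1.5 mg once weekly for the first 4 weeks". This applies in both the 3.0 mg and the 4.5 mg arm. Algorithm 2 begins at 0.75 mg for two weeks and then moves to 1.5 mg. For the other two arms Protocol 7.2.1 states: "Patients assigned to dulaglutide 1.5 mg or placebo will begin administering treatment as assigned at Visit 3, without titration". Protocol Table GBGJ.2 (Study Treatments) gives every patient a single injection per week in Weeks 0-3.

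**Allocation.** SAP 5.2 plans to "attain approximately 300 patients randomized to the 4 treatment arms in a 1:1:1:1 ratio", and within each investigational arm "approximately 38 patients will be assigned to each titration algorithm (Algorithms 1 and 2". SAP 5.3 confirms the split: "Within the dulaglutide 4.5 mg and 3.0 mg arms, patients will be randomly assigned (1:1) to Algorithm 1 or Algorithm 2".

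**GI analysis.** SAP 6.13.5 reports incidence for each randomised arm, each of the four dose-by-algorithm cells, Algorithm 1 and Algorithm 2, over 18 weeks, over the first 6 weeks and by visit. The stated purpose is "to compare the effects of the 4 different dose escalations (2 algorithms for each of the 2 investigational doses", and also to compare the two algorithms and the randomised treatments overall. SAP 6.1 defines the algorithm grouping across the two investigational doses and keeps 1.5 mg as a separate active comparator. The algorithm objective in SAP Table GBGJ.1 likewise sets 1.5 mg and placebo apart, at 6 and 18 weeks.

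**Use of the result.** Protocol 5.4 says that GI exposure-response information from this study, combined with earlier studies, will guide the final algorithm "to determine the starting dose(s), titration step(s), and duration of titration".

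**The concern.** The starting dose is one of the Phase 3 design choices that the trial is meant to inform, and Protocol 5.5 says that the onset of nausea and vomiting diminishes by 4 to 6 weeks of treatment. The first weeks are therefore the informative ones. In that window three randomised groups take the same product, strength and number of injections, yet the planned groupings never put them together. Half of the patients randomised to a 1.5 mg start stay outside any single contrast with the 0.75 mg starters.

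The named 6-week window does not isolate the starting dose either, because it includes the Week 4 step to 3.0 mg under Algorithm 1. What is at stake is precision on a small exploratory question, not the validity of a planned result.

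**Working it through.** **1. The plan's own figures.** 300/4 = 75 per arm and 75/2 = 37.5, stated as 38 per algorithm cell. On completers, SAP 5.2 says: "Assuming a 20% dropout, this will result in approximately 60 patients per arm and 30 patients per algorithm". This checks: 75 × 0.8 = 60 and 38 × 0.8 = 30.4. The only stated power is at least 90% for HbA1c. With 60 per arm, difference 1.0 and SD 1.2, the SE is 1.2 × √(2/60) = 0.219. Then 1.0/0.219 − 1.96 = 2.60, so power is 99.5% and the claim holds. No sample size or power is stated for any GI comparison.

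**2. Regimens side by side (Protocol Table GBGJ.2).**

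| Group | n | Weeks 0-1 | Weeks 2-3 | Weeks 4-5 |
|---|---|---|---|---|
| 3.0 and 4.5 mg, Algorithm 1 | 38 + 38 | 1 × 1.5 mg | 1 × 1.5 mg | 2 × 1.5 mg |
| 1.5 mg arm | 75 | 1 × 1.5 mg | 1 × 1.5 mg | 2 × 0.75 mg |
| 3.0 and 4.5 mg, Algorithm 2 | 38 + 38 | 1 × 0.75 mg | 1 × 1.5 mg | 2 × 0.75 mg |

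The first two rows are identical until the Week 4 dose and differ from then on. All groups come from one double-blind randomisation, stratified by HbA1c and blocked by country, so combining the two rows before Week 4 keeps a randomised comparison.

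**3. Counts.** A 1.5 mg start has 38 + 38 + 75 = 151, about 150. A 0.75 mg start has 38 + 38 = 76, about 75. The planned contrasts that separate the starts are Algorithm 1 v Algorithm 2 and the 1.5 mg arm v Algorithm 2, each about 75 v 75; cell-level contrasts are smaller. Safety uses the ITT population (randomised and dosed), so the randomised counts apply rather than the completer counts.

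**4. Precision.** The SE factor is √(1/n₁ + 1/n₂).

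- 75 v 75: √(2/75) = 0.163
- 150 v 75: √(1/150 + 1/75) = 0.141
- Ratio: 0.141/0.163 = 0.866, so the SE factor falls by 13% and the variance factor by 25%
- Equivalent balanced size: 2/(1/150 + 1/75) = 100 per group

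**5. Power.** The incidences are assumptions; the documents give none for these starts. SAP 6.1 uses the chi-square test when expected counts allow, and Fisher's exact test otherwise. At 10% v 20% with 75 per group the smallest expected count is 75 × 0.15 = 11.25, so chi-square applies. Two-sided 5%:

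| 0.75 mg v 1.5 mg start | 75 v 75 | 75 v 150 | Gain (points) |
|---|---|---|---|
| 10% v 20% | 41% | 49% | 8 |
| 12% v 25% | 55% | 65% | 10 |
| 15% v 30% | 60% | 71% | 11 |
| 20% v 30% | 29% | 35% | 6 |

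The first three rows are exact binomial enumeration of the chi-square test. The last is the pooled-variance normal approximation, and exact enumeration agrees with it to within a point. As an interval, at 10% v 25% the 95% half-width 1.96 × √(p₁q₁/n₁ + p₂q₂/n₂) falls from 11.9 to 9.7 percentage points.

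**The case against.** **The plan is right for its stated comparisons.** No analysis in the SAP is labelled a starting-dose comparison. SAP 6.13.5 and SAP Table GBGJ.1 compare whole escalation schemes and algorithms over 6 and 18 weeks, and over those windows the 1.5 mg arm cannot be pooled with Algorithm 1. This stands. A reader might infer that a planned GI estimate is biased or that a planned analysis is defective; the documents do not support that.

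**The 1.5 mg arm is not discarded.** It is reported beside the algorithms by visit, with visits at Weeks 2 and 4, and in the nausea time-course plot. Protocol 5.4 also sends the starting-dose question to exposure-response work, Protocol 10.3.5 includes nausea and vomiting in the PK/PD analyses, and SAP 6.12 puts the details in a separate plan. That route can use all patients. This stands too: the loss is confined to the direct GI contrasts in the SAP.

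**The dose differs for only two weeks.** In Weeks 2-3 all three groups take 1.5 mg, so a halving of incidence over four weeks may be generous. This stands. Smaller differences lower both power figures, as the 20% v 30% row shows.

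**The gain is easy to overstate.** A reader using an unpooled-variance normal approximation would get 41 to 56%, 55 to 71% and 61 to 77% for the first three rows, a gain of 15 to 16 points. That method inflates power when the larger group has the higher incidence, and it is not the test in SAP 6.1.

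None of this removes the core fact that about 75 more patients randomised to the same early regimen could enter the contrast. The SAP already applies the principle: for pancreatic enzymes and ECG it combines the 3.0 and 4.5 mg cells by algorithm at Week 6, when those cells have had the same titration doses.

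**Conclusion.** The point holds as a missed efficiency in an exploratory comparison. The regimen identity and the counts come directly from the documents. The 13% cut in the SE factor and 25% cut in variance follow from the counts alone. The power gain of about 6 to 11 points rests on assumed incidences and would be smaller in absolute terms if the starts differ little.

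Pooling is valid only for events with onset before the Week 4 dose, and the contrast in Weeks 0-3 is between starting regimens, not between constant doses. No stated figure is wrong, no passages conflict, and SAP 6.5 already treats the trial as exploratory. The change is worth making because it is cheap, but it is optional.

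**What to change.** Add to SAP 6.13.5 one prespecified exploratory table of nausea, vomiting and diarrhea with onset before the Week 4 dose, by randomised starting regimen:

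- 1.5 mg start: both Algorithm 1 cells plus the 1.5 mg arm, about 150
- 0.75 mg start: both Algorithm 2 cells, about 75
- placebo: about 75

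Show Weeks 0-1 separately, since the dose differs only there. Set the cut-offs by dose date rather than visit number, and label the table as not applicable to the 6- and 18-week windows. All existing tables stay as they are.

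The cost is one extra table from data already collected, limited to the first four weeks. SAP 6.1 would allow such an analysis even after datalock, but fixing the grouping and the window in advance avoids a post hoc choice.

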6.13.6. Treatment of Overdose

A study drug overdose (more than the specified number of injections, whether for placebo or dulaglutide treatment) will be reported as an AE. This AE will be summarized only if it occurs with more than 3% of patients. Otherwise, only a data listing will be generated including the actual dose data (Section 6.13.1) along with treatment overdose AE reported date.

6.13.7. Cardiovascular Safety

6.13.7.1. Cardiovascular Events

Listings and summaries of adjudicated and investigator-reported CV events will be provided. The summary report for adjudicated and investigator-reported CV events will only be generated if more than 3% patients have the events. The test statistics are detailed in Section 6.1.

6.13.7.2. Electrocardiograms

Heart rate (HR), PR interval (PR), and QT corrected for heart rate using QTcF are collected in triplicates. Prior to any analysis, the arithmetic mean from the three measures for the same parameter at the same visit will be calculated and use for all subsequent analysis. MMRM model detailed in Section 6.1. for continuous variable analysis will be used to analyze each parameter in change from baseline. The treatment in the model will be placebo, dulaglutide 1.5 mg, dulaglutide 3.0 mg/algorithm 1, dulaglutide 3.0 mg/algorithm 2, dulaglutide 4.5 mg/algorithm 1, dulaglutide 4.5 mg/algorithm 2.

The reports for these analyses will include:

- LS means and corresponding 95% CIs for each randomized treatment at each scheduled visit, and the difference in LS means, corresponding 95% CI along with p-value compared to placebo and to dulaglutide 1.5 mg at the same visit.
- LS means and corresponding 95% CIs of each parameter's effect for algorithm 1, algorithm 2, and the difference between algorithm 2 and algorithm 1 (using algorithm 1 as reference) at Week 6 (Visit 6). These results will not be acquired directly from the MMRM model. Rather, they will be obtained from the same model by forming appropriate estimate statements with the same algorithm across dulaglutide 3.0 mg and dulaglutide 4.5 mg.
- LS means and corresponding 95% CIs of each parameter's effect for dulaglutide 3.0, dulaglutide 4.5, and the difference between each combined treatment across algorithms and Placebo, and the difference between each combined treatment to Dula 1.5 at the same Week (Visit): Week 8 (Visit 8), Week 10 (Visit 10) and Week 18 (Visit 12). These results will be obtained through the same model by forming appropriate estimate statements for the same dose across different algorithms.
- The difference in LS means and the corresponding 95% CIs along with the p-value between each maintenance visit (Week 8/Visit 8, Week 10/Visit 10, Week 18/Visit 12) and the end of titration (Week 6/Visit 6) within the same treatment including the combined dulaglutide 3.0 mg and 4.5 mg, and within the same algorithm will be presented. Any result related to combined treatment across algorithms and each algorithm at Visit 6 (Week 6) will be formed by constructing an appropriate estimate statement.

The threshold analysis will only include HR, PR by visit and by randomized treatment, dulaglutide 3.0, and dulaglutide 4.5 mg. The threshold is defined in [Table GBGJ.3](#).

Table GBGJ.3. Heart Rate, PR-Interval, and QTcF Abnormal Data

Parameter (Unit)	Visit	Threshold definition
HR (bpm)	Baseline (Visit 1)	>100, ≥ 130
	Post baseline	>100 and CFB >15
PR (msec)	Baseline (Visit 1)	≥ 220
	Post baseline	≥ 220
		≥ 220 and (%CFB >0 and $\leq 25\%$)
		≥ 220 and (%CFB >25%)
QTcF	Baseline (Visit 1)	> 450 (Male) or > 470 (Female)
		> 480
		> 500
	Post baseline	> 450 (Male) or > 470 (Female)
		> 480
		> 500
		>30 CFB
		>60 CFB

Abbreviations: QTcF = Fridericia's corrected QT interval.

Note: CFB means change from baseline; and %CFB is the percentage change from baseline.

The qualitative summary related to the treatment-emergent cardiac conduction and rhythm abnormalities will be reported by treatment. The abnormal ECG outcomes will be listed by treatment and patient.

A non-ITP Bayesian model will be fitted detailed in Section 6.11.2.3 with the priors: $\alpha, \beta[i, t] \sim N(0, 100)$ using 10000 MCMC samples with thin=10 and burn-in=10000. The probability of the posterior distribution of the parameter of interest on heart rate increase from baseline of each investigational dulaglutide dose compared to Dula 1.5 mg at Week 18.

$$pr(\Delta_i - \Delta_{dula1.5mg} < \text{threshold})$$

i stands for dulaglutide 3.0 mg/algorithm 1, dulaglutide 3.0 mg/algorithm 2, dulaglutide 4.5 mg/algorithm 1, and dulaglutide 4.5 mg/algorithm 2.

The threshold for this analysis will be 3bpm, 5 bpm, 7 bpm, 10 bpm.

The probability for Week 26 will be assumed to be the same as Week 18 from this model. The algorithm comparison at Week 6 will be evaluated.

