- j A serum pregnancy test will be performed at Visit 1 for women of childbearing potential only.
- k A urine pregnancy test will be performed at Visit 3 with the result available prior to randomization and first injection of study drug for women of childbearing potential only. Additional pregnancy tests may be performed at the investigator's discretion during the study.
- l Follicle-stimulating hormone test performed at Visit 1 for postmenopausal women at least 50 years of age with an intact uterus, not on hormone therapy, and who have had spontaneous amenorrhea for more than 6 months and less than 12 months. After Visit 1, additional tests may be performed at the investigator's discretion during the study.
- m For Visit 3, Visit 6, Visit 10, Visit 12, Visit 801, and the ET visit, patients should be reminded to report to the site in a fasting condition, after a period of approximately 8 hours without eating, drinking (except water), or any significant physical activity and before taking their OAMs (if used).
- n Urinary albumin and creatinine are measured; the ratio is calculated.
- o The CKD-EPI equation will be used by the central laboratory to estimate and report eGFR. Values that are  $<60$  mL/min/1.73 m^2 at Visit 1 must be retested at Visit 2. If the highest of the 2 values is lower than the cutoff value for discontinuation of metformin per country-specific label (for example,  $<45$  mL/min/1.73 m^2 or  $<60$  mL/min/1.73 m^2), the patient will be discontinued from the trial prior to randomization. After randomization (Visit 3), values that are  $<60$  mL/min/1.73 m^2 must be first confirmed on a retest before any protocol-required treatment adjustment is implemented.
- p Collect sample in P800 tube. Aliquot samples, 1 for glucagon and the remainder for nonpharmacogenetic biomarker.
- q PK samples at Visit 3 and Visit 5 should be collected 1-24 hours post-injection of study drug.
- r PK sample at Visit 4 should be collected immediately prior to administration of study drug.
- s PK sample at Visit 6 should be collected 5-7 days (120-168 hours) post-injection of Week 5 study drug or just pre-injection of Visit 6 study drug.
- t PK sample at Visit 10 should be collected 1-4 days (24-96 hours) post-injection of Visit 10 study drug.
- u PK samples at Visit 12, Visit 801, and the ET visit can be collected at any time during the visit.

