With respect to HR elevations, treatment with dulaglutide 0.75 mg or 1.5 mg for 26 weeks increases HR in the range between 2 and 4 beats per minute (bpm), with no clinically relevant cardiovascular (CV) safety findings (Trulicity USPI [WWW]; Ferdinand et al. 2016). The estimated effect of the 3.0 mg dose on HR at 26 weeks, based on a small number of patients with mean exposure of approximately 9.2 weeks in Study GBCF, was an increase of approximately 5 bpm (data on file). No safety data are available after 26 weeks of treatment for doses greater than 3.0 mg. Increases in HR with dulaglutide are time-dependent and diminish over time (data on file). The ongoing REWIND CV outcome trial (H9X-MC-GBDJ) will provide data on the long-term effect of dulaglutide on the CV risk.

The results from recently reported studies of dulaglutide described above have provided understanding of the clinical relevance of the pancreatic enzyme elevations and increases in HR, which was not available at the time of development of dulaglutide for initial registration (Egan et al. 2014). The additional data did not suggest association between these findings and long-term safety outcomes, providing support for re-evaluation of a range of once weekly dulaglutide doses higher than the currently approved 0.75 mg and 1.5 mg doses to assess whether an additional dose with favorable benefit/risk profile compared to the approved doses can be developed.

The investigational dulaglutide doses to be studied in Study GBGJ (3.0 mg and 4.5 mg) were chosen based on simulations which included data collected in Studies H9X-MC-GBCD (GBCD) and GBCF (Barrington et al. 2011, Skrivanek et al. 2014). The results of these simulations suggest that these doses may provide an incremental, clinically relevant improvement in Hb1Ac and body weight reduction in comparison to the 1.5 mg dose after 26 weeks. Further information on the rationale for the doses included in this study is provided in Section 5.5.

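### The planned inference on change from Week 6 (ECG, vital signs, pancreatic enzymes) is within-arm only; add the difference in change against dulaglutide 1.5 mg and placebo, and do not read the pooled 3.0 mg or pooled Algorithm 1 change as one dose step

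*SAP*

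**What the plan says.** The fourth reporting bullet of SAP 6.13.7.2 (heart rate, PR interval, QTcF) calls for "The difference in LS means and the corresponding 95% CIs along with the p-value between each maintenance visit" (Weeks 8, 10 and 18) on one side. The reference on the other side, and the level of the contrast, read "and the end of titration (Week 6/Visit 6) within the same treatment including the combined dulaglutide 3.0 mg and 4.5 mg"; the same contrast is also to be given by algorithm. The model's treatment factor has six levels: placebo, 1.5 mg, and the four dose-by-algorithm cells. SAP 6.13.7.3 reports pulse rate and blood pressure in the same way. SAP 6.13.4.3 item 4 does so for pancreatic amylase and lipase, as a ratio of Week 18 to Week 6.

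The controlled comparisons in 6.13.7.2 are same-visit ones: LS-mean differences with "corresponding 95% CI along with p-value compared to placebo and to dulaglutide 1.5 mg at the same visit" for each randomized treatment, and for the combined doses at Weeks 8, 10 and 18.

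Three parts of the protocol bear on the change from Week 6.

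- **Sampling time (Section 2, footnotes s and t).** "PK sample at Visit 6 should be collected 5-7 days (120-168 hours) post-injection of Week 5 study drug", or just before the Visit 6 dose. By contrast, "PK sample at Visit 10 should be collected 1-4 days (24-96 hours) post-injection of Visit 10 study drug". Footnote d and Section 9.5 tie the ECG to the PK sample.
- **Titration (Section 5.1).** The first of the two algorithms reads: "patients will receive dulaglutide 1.5 mg once weekly for the first 4 weeks followed by dulaglutide 3.0 mg once weekly for the next 2 weeks".
- **Time course (Section 3.2).** "Increases in HR with dulaglutide are time-dependent and diminish over time (data on file").

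**The concern.** A change from the end of titration to a maintenance visit invites the reading that it shows what moving to the maintenance dose does to heart rate, QTcF, blood pressure or enzymes. Within one arm, that change also contains whatever else differs between the two visits. For heart rate the protocol itself names one such thing, waning over time. At Week 10 there is a second, because the ECG falls at a different point in the dosing interval. Dulaglutide 1.5 mg keeps a constant dose over the same visits, so it can show both without any step.

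Pooling adds a separate difficulty. Half of the 3.0 mg arm is already on 3.0 mg before Week 6, so the combined 3.0 mg change does not describe one dose step.

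The stake is interpretive. The trial is meant to guide Phase 3 dose selection, and heart rate was among the effects that led to early discontinuation of the 3.0 mg arm in the earlier dose-finding study (Protocol 3.2). A p-value on an uncontrolled change could suggest a step effect where there is none, or hide one behind waning.

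**Working it through.** **1. Nominal step at Week 6** (Protocol Table GBGJ.2: maintenance dose minus dose in Weeks 4 and 5)

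| Cell | Weeks 4–5 | From Week 6 | Step |
|---|---|---|---|
| 3.0 mg, Algorithm 1 | 3.0 | 3.0 | 0 |
| 3.0 mg, Algorithm 2 | 1.5 | 3.0 | +1.5 |
| 4.5 mg, Algorithm 1 | 3.0 | 4.5 | +1.5 |
| 4.5 mg, Algorithm 2 | 1.5 | 4.5 | +3.0 |
| 1.5 mg | 1.5 | 1.5 | 0 |
| Placebo | 0 | 0 | 0 |

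Allocation to algorithms is 1:1. The combined 3.0 mg and pooled Algorithm 1 contrasts each average (0 + 1.5)/2 = 0.75 mg. The combined 4.5 mg and pooled Algorithm 2 contrasts each average (1.5 + 3.0)/2 = 2.25 mg. If only the step mattered, an effect d in 3.0 mg/Algorithm 2 would appear as d/2 in the combined 3.0 mg estimate. The protocol's heart-rate figures (2 to 4 bpm at 0.75 or 1.5 mg, about 5 bpm at 3.0 mg, both at 26 weeks) suggest d of roughly 5 − 4 = 1 to 5 − 2 = 3 bpm, which would show as 0.5 to 1.5 bpm.

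**2. Time since injection at each ECG visit** (Protocol Section 2; nominal days from SAP Appendix 1)

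- Week 6: nominal Day 43, window −3 days; Week 5 dose nominally Day 36. The visit falls (40 − 36) × 24 = 96 to (43 − 36) × 24 = 168 h after that dose. Footnote s narrows the PK sample to 120–168 h, or just pre-dose.
- Week 8: ECG, but no PK sample and no time stated relative to the dose.
- Week 10: nominal Day 71, window +4 days. Footnote t puts the PK sample 24–96 h after that week's dose.
- Week 18: sample at any time. Nominal Day 127 is (127 − 120) × 24 = 168 h after the Week 17 dose, the same phase as Week 6.

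The mismatch is therefore documented for Week 10 against Week 6 only. Protocol 9.4.1.3 takes vital signs before the ECG and blood draw at the same visit, so pulse rate and blood pressure probably share it.

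**3. The plan's own figures.** Completers: 75 × 0.8 = 60 per arm and 37.5 × 0.8 = 30 per algorithm, as stated. HbA1c power: 1.0/(1.2 × √(2/60)) = 4.56 and Φ(4.56 − 1.96) = 99.5%, consistent with the stated 90% or more. No precision or power is given for ECG or vital-sign contrasts.

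**4. How often a pure drift is declared significant.** Let b be a drift with no step effect, SD the between-patient SD of the change between two visits, and SE = SD/√n. The rejection rate is Φ(b/SE − 1.96) + Φ(−b/SE − 1.96). The documents give neither SD nor b. I assume SD 6, 8 or 10 bpm and b of 1 or 2 bpm.

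| SD | SE, n = 60 | b = 1 | b = 2 |
|---|---|---|---|
| 6 | 0.77 | 25% | 73% |
| 8 | 1.03 | 16% | 49% |
| 10 | 1.29 | 12% | 34% |

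In one algorithm cell (n = 30) the rates are 15%, 10.5% and 8.5% for 1 bpm, and 45%, 28% and 19% for 2 bpm.

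**5. Precision of the controlled change.** SE = SD × √(1/n₁ + 1/n₂). For 60 versus 60 this is 1.10 to 1.83 bpm, √2 = 1.41 times the within-arm SE. For one cell of 30 against 60 it is 1.34 to 2.24 bpm, √3 = 1.73 times the SE of a whole-arm change.

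**The case against.** The strongest reply is that the SAP does not present this bullet as the test of the dose step. It is one of four outputs, and controlled comparisons surround it. Same-visit differences from placebo and 1.5 mg are reported, at Week 6 as well for the randomized treatments. The placebo and 1.5 mg changes from Week 6 will be shown, because both are treatments in the model. On a natural reading, 3.0 mg/Algorithm 2 also gets its own line. Posterior probabilities against 1.5 mg are planned for each cell at Week 18, and Protocol 10.3.5 relates concentration to QT, BP and HR. All of this stands. A reader might infer that the control arms go unused; they do not. The point estimate of the controlled change is a subtraction of planned outputs, and its SE could be approximated from the two within-arm CIs. What is missing is that estimate with its own prespecified CI and p-value, while the uncontrolled change has both.

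A reader might also extend the timing mismatch to every maintenance visit. The documents do not support that. Week 8 has no stated time since dose, Week 18 is nominally in the same phase as Week 6, and the enzyme contrast uses only Week 18. The Week 10 timing is itself inferred from the PK sample. Footnote d sets a minimum lead of 30 minutes with no upper limit, whereas Section 9.5 sets a maximum gap of 30 minutes.

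Nor would a controlled contrast remove everything. Waning and time since injection are drug effects, so subtracting placebo removes neither. Subtracting 1.5 mg removes only the part common to both doses.

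Finally, 2 bpm is large against the 2 to 4 bpm quoted for approved doses, and both it and the SD are assumptions.

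**Conclusion.** The point holds in a limited form. The only CI and p-value specified for the change from end of titration come from an uncontrolled contrast. For heart rate, that contrast mixes a step effect with a time trend that the protocol acknowledges. For Week 10 ECGs, and probably vital signs, it also mixes in time since injection. For enzymes, only the lack of a control and the pooling apply.

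The averaging of 0 and +1.5 mg in the combined 3.0 mg and pooled Algorithm 1 contrasts follows directly from Table GBGJ.2. It concerns nominal dose: after two 3.0 mg doses, exposure in Algorithm 1 may still be rising, so a zero step does not guarantee a zero change.

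The size is conditional. With 60 per arm and an assumed SD of 6 to 10 bpm, the chance of p≤0.05 with no step effect is 12% to 25% for a 1 bpm drift and 34% to 73% for 2 bpm, against a nominal 5%. The actual drift cannot be computed from the documents. Because these are exploratory safety outputs without multiplicity control, it would be wrong to infer a threat to the trial's conclusions. The primary HbA1c analysis is untouched, and the interim heart-rate and pulse criteria compare the higher doses with placebo. It is a cheap improvement and worth making.

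**What to change.** - **Add the controlled change.** From the same six-cell MMRM, add ESTIMATE statements for [Week 8, 10 or 18 minus Week 6] in each dose-by-algorithm cell minus the same change in dulaglutide 1.5 mg, and minus placebo, with 95% CI and p-value. Apply this to ECG and vital signs. For enzymes, report the ratio of ratios at Week 18 versus Week 6.
- **Make the within-arm changes descriptive.** Keep them in the tables, without p-values.
- **Limit the pooled contrasts.** State that the combined 3.0 mg and pooled-algorithm changes from Week 6 are not to be read as the effect of one dose step.
- **State what remains confounded.** Subtracting 1.5 mg removes drift common to both doses, not a peak-to-trough difference that grows with dose. Week 10 minus Week 6 should be read with caution and alongside the planned PK/PD analysis.
- **Reconcile the ECG timing rules.** Footnote d of the Schedule of Activities and Protocol 9.5 agree only at exactly 30 minutes.

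The cost is SAP wording and a few statements, with no new data or visits. The controlled contrast is less precise: its SE is about 1.4 times the within-arm SE for 60 versus 60, and 1.73 times the whole-arm SE for a single algorithm cell, so many of these intervals will be wide.
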